3.3. Statistical Arrangements

1) Summary statistics

For quantitative variables, summary statistics are number of relevant patients, mean, standard deviation, minimum, quartile points (25 percentile, 50 percentile, and 75 percentile), and maximum.

2) Number of digits to be displayed

Proportions and rates will be expressed as percentage (%) and displayed to two decimal places by rounding.

Minimum and maximum will be displayed with the same number of digits as raw data, and the other

summary statistics will be displayed to one lower digit than raw data by rounding.

Ninety-five percent confidence interval will be displayed with the same number of digits as the relevant statistics.

Statistical p-value will be displayed to four decimal places by rounding. P-value less than 0.0001 will be displayed as <0.0001. Infeasibility of testing will be indicated as “-.”

3) 95% confidence interval

All confidence intervals will be presented as two-sided confidence intervals.

4) Rules of statistical testing

One-sample t-test or one-sample Wilcoxon test will be used for pre- and post-treatment comparison of continuous variables.

McNemar test will be used for pre- and post-treatment comparison in shift tables.

A two-sided 5% level of significance will be used.

The category of “unknown” will be excluded from statistical testing.

4. Analysis Sets

4.1. Enrolled Patients

All patients for whom the patient registration form has been accepted

4.2. Patients with the CRF Collected

Patients for whom the CRF has been collected and finalized

4.3. Patients Evaluated for Safety

All patients with the CRF collected, excluding those who meet any of the following criteria:

- 1) Not treated with Benet/Actonel
- 2) Unknown whether an AE occurred
- 3) Deviated from the registration criteria
 - Treated before conclusion of a contract
 - Not registered in the registration period
 - Failed to fax the patient registration form within 15 days after the first prescription of Benet/Actonel
 - Other (assessed as deviated from the registration criteria due to any reason not listed above)

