9.2.5 Assessment of Vertebral Fracture

1) Surveillance items

Vertebral fracture before the start of Benet treatment (baseline) will be confirmed, and the date of radiography, radiographic location, and location of vertebral fracture will be entered into the CRF. Then, the presence or absence and location of new vertebral fracture, presence or absence of worsening of prevalent vertebral fracture, and presence or absence of apparent trauma during treatment and at the end of the observation period (or discontinuation of treatment) relative to baseline will be entered into the CRF.

2) Time points of surveillance

At the start of Benet treatment, 12, 24, and 36 months after the start of treatment (or discontinuation of treatment), and when vertebral fracture is suspected during the observation period

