9.2.6 Assessment of Non-vertebral Fracture

1) Surveillance items

Non-vertebral fracture during Benet treatment involving the femur, wrist, forearm, upper arm, pelvis, lower limb, etc. will be entered into the CRF. Confirmed non-vertebral fracture will be handled as an adverse event, and the fracture site, date of fracture (date of onset), presence or absence and details of apparent trauma, seriousness, reason for seriousness, presence or absence of discontinuation of Benet treatment, date of outcome assessment, outcome, and causal relationship to Benet will be entered into the CRF.

2) Time points of surveillance

12, 24, and 36 months after the start of Benet treatment (or discontinuation of treatment) and when non-vertebral fracture is confirmed during the observation period

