9.3 Adverse Events (AEs)

1) Surveillance items

Presence or absence of AE (refer to Table 1), AE term, date of onset, seriousness and reason for seriousness (refer to Table 2), presence or absence of discontinuation of Benet treatment, date of outcome assessment, outcome, causal relationship to Benet* (refer to Table 3)

Patients with “not resolved” or “unknown” outcome or “unevaluable” causal relationship should be followed up wherever possible.

Any new vertebral fracture or worsening of prevalent fracture during treatment will be entered into the adverse event column.

The following events will also be entered into the adverse event column: upper gastrointestinal disorder, hepatic function disorder/jaundice, osteonecrosis of jaw/osteomyelitis of jaw, atypical fracture of subtrochanteric section of femur or shaft of proximal femur, musculoskeletal pain, atrial fibrillation, esophageal carcinoma, and gastrointestinal disorders including diarrhea.

* For the causal relationship to Benet, the rationale for “not related” and the reason for “unevaluable” shall be collected.

2) Time points of surveillance

12, 24, and 36 months after the start of Benet treatment (or discontinuation of treatment) and when an AE is confirmed during the observation period

Table 1 Definition of adverse events

An AE is defined as any untoward medical occurrence in a clinical investigation subject administered a drug; it does not necessarily have to have a causal relationship with this treatment.

An AE can therefore be any unfavorable or unintended sign (e.g., abnormal laboratory finding), symptom, or disease temporally associated with the use of a drug, whether or not it is considered related to the drug.

The following are also handled as AEs:

- Symptoms and so forth that occur in infants breast-fed by their mothers under treatment with a drug
- Symptoms and so forth that occur in children treated with a drug
- Symptoms and so forth that occur after administration or self-administration of a drug at higher doses than the approved dose

Table 2 Criteria for assessing seriousness

An AE satisfying any of the following is assessed as serious:

1. Results in death (death)
2. Is life-threatening (risk of death)
3. Requires inpatient hospitalization or prolongation of existing hospitalization (hospitalization/prolonged hospitalization)
4. Results in persistent or significant disability/incapacity (disability)
5. Leads to a congenital anomaly/birth defect (congenital anomaly)

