3.2. Definitions of Terms

| Term | Description |
|-----------------------------|--|
| Finalized patient | For Benet Tablets, a finalized patient is defined as a patient who has the date of CRF approval in the PMS system. For Actonel Tablets, a finalized patient is defined as a patient who has the date of temporary finalization in the business management system. |
| Adverse event (AE) | All events entered into the column of [Adverse event] or [Assessment of non-vertebral fracture] in the case report form (CRF) Any unfavorable or unintended sign (e.g., abnormal laboratory finding), symptom, or disease temporally associated with the use of Benet/Actonel, whether or not it is considered related to Benet/Actonel |
| Adverse drug reaction (ADR) | All adverse events except those not related to Benet/Actonel according to “Causal relationship to Benet/Actonel” both in the column of [Adverse event] or [Assessment of non-vertebral fracture] in the CRF and determined by the company If either assessment is missing, non-missing assessment of causal relationship is confirmed to determine the adverse event as an adverse drug reaction unless not related to Benet/Actonel. |
| Serious adverse event (SAE) | Adverse event assessed as serious according to “Seriousness” at least either in the column of [Adverse event] or [Assessment of non-vertebral fracture] in the CRF or determined by the company, including “AEs that must always be assessed as serious” in the implementation guidelines and AEs in Takeda Medically Significant AE List |

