4.4. Patients Evaluated for Efficacy

All patients evaluated for safety, excluding those who meet the following criterion:

Pre- and post-baseline values of all efficacy endpoints (bone turnover markers, bone mineral density, vertebral fracture, non-vertebral fracture, height, and low back pain) are unknown, including incalculable values

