4.5. Patients Evaluated for Vertebral Fracture

All patients evaluated for efficacy, excluding those who meet any of the following criteria:

1) No evidence of 1 to 4 fractures from the fourth thoracic vertebra to the fourth lumbar vertebra provided by thoracic and lumbar spinal radiography performed before the start of the surveillance^{*}

* The permissible range before the start of the surveillance is Days -90 to 1.

2) Not 50 years or older

3) Not an outpatient who can walk

4) No known date of pre- or post-treatment^{*} radiography for assessment of vertebral fracture

* For the permissible range before or after treatment, refer to *1 in Section 6.3.1.

5. Handling of Data

Handling of data for analysis is described below. Details of processing will be specified in separately prepared analysis data set specifications.

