5.1. Handling of Dichotomous Variables

For dichotomous variables, the presence or absence will be determined as described below when there is a column for details to be specified for “Yes.”

- 1) “Yes” when details are specified
- 2) “No” when no details are specified and “No” is checked
- 3) “Unknown” when neither 1 nor 2) is applicable

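### Unknown adverse event status removes patients from the fracture analyses, and a properly entered fracture itself settles that status

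*SAP*

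**What the plan says.** All SAP references are to the current plan, version 5.1.

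- **The criterion.** SAP Section 4.3, criterion 2, excludes a patient from the safety set if it is "Unknown whether an AE occurred".
- **The nesting.** Section 4.4 defines the efficacy set as "All patients evaluated for safety, excluding those who meet the following criterion". Section 4.5 defines the vertebral fracture set as "All patients evaluated for efficacy, excluding those who meet any of the following criteria". Neither section lifts criterion 2.
- **Fractures are adverse events.** Protocol 9.3: "Any new vertebral fracture or worsening of prevalent fracture during treatment will be entered into the adverse event column". Protocol 9.2.6: "Confirmed non-vertebral fracture will be handled as an adverse event". SAP Section 3.2 defines an AE as "All events entered into the column of [Adverse event] or [Assessment of non-vertebral fracture] in the case report form (CRF").
- **The vertebral endpoint has its own record.** Protocol 9.2.5 collects the "presence or absence and location of new vertebral fracture, presence or absence of worsening of prevalent vertebral fracture" in a separate assessment. Section 3.2 of the SAP does not list that assessment as a source of AEs.
- **How a yes/no item becomes unknown.** Under SAP Section 5.1 an item with a details field is *Yes* if details are given, *No* if there are none and *No* is ticked, and *Unknown* "when neither 1 nor 2) is applicable". Section 5.5 confirms that the patient-level AE variable has an unknown level.
- **Reporting.** Exclusions and their reasons are counted (6.1.1) and listed by patient (6.4.2).

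**The concern.** Entry to an analysis set should not depend on the outcome being analysed. Here it can. A fracture entered as the protocol instructs supplies AE details, so that patient's AE status is known and criterion 2 cannot apply. A patient with baseline and follow-up films, no fracture, and an AE item that was neither ticked nor completed can be classed as unknown and removed from every fracture analysis, although fracture status is known.

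If that is the usual pattern, events stay and event-free patients leave. The incidence estimates, including the primary one, are then pushed up by a gap in a safety field.

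**Working it through.** **The plan's own figure.** Protocol 3.2 needs about 250 analysable patients and expects 50% dropout: 250 / (1 − 0.5) = 500, which reproduces. The documents give no fracture rate and no count of AE-unknown patients, so incidence p and the share u dropped by criterion 2 are assumptions below.

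**Crude proportion.** If a share u of otherwise evaluable patients is dropped and all are event-free, incidence moves from p to p / (1 − u).

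- p = 15%, u = 5%: 0.15 / 0.95 = 15.79%, a rise of 0.79 points.
- p = 15%, u = 1%, 2%, 10%: 15.15%, 15.31%, 16.67%.
- Over p = 5% to 20% and u = 1% to 10%, the rise runs from 0.05 to 2.2 points. At u = 0 it is zero.
- Sampling error for comparison: 1.96 × √(0.15 × 0.85 / 250) = 4.4 points.

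**Kaplan-Meier, the estimator in SAP 6.3.1.** Event-free patients are censored at their last negative film, so the effect depends on when that film was taken. A simulation used 500 patients, films at Days 360, 720 and 1096, a constant fracture probability per interval giving p = 15% at three years, about 50% dropout, and 300 replicates. In each, 25 event-free patients (u = 5%) were given the stated last film and then either kept or dropped.

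| Last negative film of dropped patients | Kept (%) | Dropped (%) | Difference (points) |
|---|---|---|---|
| Day 100 | 15.87 | 15.87 | 0.00 |
| Day 360 | 15.61 | 15.86 | 0.25 |
| Day 720 | 15.26 | 15.84 | 0.58 |
| Day 1096 | 14.61 | 15.60 | 0.99 |

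Hand check of the Day 360 row: the per-interval probability is 1 − 0.85^(1/3) = 5.27%. Dropping 25 of 500 from that risk set gives 5.27 / 0.95 = 5.55%, a difference of 0.28 points. Multiplied by survival over the next two intervals, 0.9473² = 0.897, this is 0.25. With p = 20%, u = 5% and a last film at Day 1096, the simulated difference is 1.35 points.

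**Can the direction reverse?** For vertebral fracture, yes, by two routes.

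1. A fracture recorded only in the vertebral assessment, with the AE item blank, is not an AE under SAP 3.2, so the patient can be classed as unknown and dropped.
2. The protocol 9.3 instruction covers fractures during treatment. SAP 6.3.1 accepts films to 90 days after the end date, and Section 5.5 sets the end date 30 days after the last dose, so films count to 30 + 90 = 120 days after it. A fracture found in that tail is not clearly under the instruction.

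As an illustration, take 38 fractures in 250 (15.2%) with 12 patients dropped:

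- none of the 12 with a fracture: 38/238 = 15.97%
- one: 37/238 = 15.55%
- two: 36/238 = 15.13%
- three: 35/238 = 14.71%

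The sign changes at two, because 12 × 0.152 = 1.8.

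**Non-vertebral fracture.** Any entry in that column is an AE by definition in SAP 3.2. If the AE variable follows that definition, no recorded case is lost by this route, and the effect is zero or upward.

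**The case against.** A reader might infer that criterion 2 can remove only fracture-free patients, so the primary incidence must be biased upward. The documents do not support that. It assumes that every vertebral fracture was copied into the AE column while AE entry was incomplete for everyone else, and the SAP has no rule enforcing the copying. The two routes above show how a primary event could be lost.

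Three further objections deserve weight.

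- **The step from a blank AE item to exclusion is partly inferred.** Section 5.1 of the SAP is expressly invoked for marked baseline items in 6.1.2, not for the AE variable in 5.5. Processing details are left to separate specifications. There are three CRFs per patient, with no stated rule for combining a blank AE item on one with completed items on the others. This stands as a limit on how often the problem arises. Criterion 2 itself, and its inheritance by 4.4 and 4.5, are explicit.
- **The effect may be nil.** Patients without dated pre- and post-treatment films leave the vertebral analyses anyway under 4.5 and 6.3.1. Only AE-unknown patients with valid films matter, and their number is not given. This stands.
- **The exclusions are visible.** The diagram in 6.1.1 and the listing in 6.4.2 give reasons. But the listing items include neither film dates nor fracture status, so it does not by itself show how many dropped patients could have been analysed. Visibility also does not restore them.

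**Conclusion.** The point holds as a minor, inexpensive improvement. The fracture sets inherit a safety criterion that is tied to the outcome, and nothing elsewhere in the plan reverses this. Where protocol 9.3 is followed, the criterion can remove event-free patients with usable films but not fracture cases, and so can raise estimated incidence. Where a vertebral fracture did not reach the AE column, it can instead discard a primary event.

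At the assumed p = 15% and u = 5%, all event-free, the size is about 0.8 points crude and at most about 1.0 point on Kaplan-Meier, well inside the sampling error. It is zero if no otherwise evaluable patient has unknown AE status. The Kaplan-Meier figures also rest on the assumed annual films and dropout pattern.

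**What to change.** In SAP Section 4.4, start the efficacy set from patients with the CRF collected who were treated and do not meet criterion 3 of Section 4.3 (registration deviations). Criterion 2 then applies to the safety set only, and Section 4.5 follows unchanged. This also keeps in vertebral fractures that never reached the AE column.

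At minimum, leave the sets as they are, report how many patients were excluded solely by criterion 2 but have valid fracture data, and add a sensitivity Kaplan-Meier analysis that includes them.

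The cost is one sentence in 4.4 and a redrawn composition diagram, using data already collected. The drawback is that the efficacy set is no longer a strict subset of the safety set, which the report should say.

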4.4. Patients Evaluated for Efficacy

All patients evaluated for safety, excluding those who meet the following criterion:

Pre- and post-baseline values of all efficacy endpoints (bone turnover markers, bone mineral density, vertebral fracture, non-vertebral fracture, height, and low back pain) are unknown, including incalculable values

4.5. Patients Evaluated for Vertebral Fracture

All patients evaluated for efficacy, excluding those who meet any of the following criteria:

1) No evidence of 1 to 4 fractures from the fourth thoracic vertebra to the fourth lumbar vertebra provided by thoracic and lumbar spinal radiography performed before the start of the surveillance^{*}

* The permissible range before the start of the surveillance is Days -90 to 1.

2) Not 50 years or older

3) Not an outpatient who can walk

4) No known date of pre- or post-treatment^{*} radiography for assessment of vertebral fracture

* For the permissible range before or after treatment, refer to *1 in Section 6.3.1.

5. Handling of Data

Handling of data for analysis is described below. Details of processing will be specified in separately prepared analysis data set specifications.

5.1. Handling of Dichotomous Variables

For dichotomous variables, the presence or absence will be determined as described below when there is a column for details to be specified for “Yes.”

- 1) “Yes” when details are specified
- 2) “No” when no details are specified and “No” is checked
- 3) “Unknown” when neither 1 nor 2) is applicable

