| Flag for employment of data | It is identified whether measurement data are employed. |
| Flag for event | A patient with event is defined as a patient who experienced at least one event such as vertebral fracture. A patient with no event is defined as a patient who experienced no event. |
| Time point of event onset | Time point of event onset is defined as the first onset of event such as vertebral fracture. Patients with no event are censored at the final assessment. |
| Measured value before the start of treatment | The measured value before the start of treatment is identified. |
| Change | Value obtained by deducting the measured value before the start of treatment from a measured value at each time point |
| Percent change (%) | Value obtained by dividing a change by the measured value before the start of treatment and then multiplying the division by 100 |
| Time of onset (days) | Number of days from the start date of Benet/Actonel treatment to the date of onset of AE “Date of onset” - “start date of Benet/Actonel treatment” + 1 |
| Flag for inclusion/exclusion as an AE | It is identified whether an event is an AE. |
| Relationship (for analysis) | It is identified whether an AE is related to Benet/Actonel. The causal relationship is handled as specified for “Adverse drug reaction” in Section 3.2. |
| Seriousness (for analysis) | It is identified whether an AE is serious. The seriousness is |

| Derived variable | Description |
|-------------------------------|--|
| | handled as specified for “Serious adverse event” in Section 3.2. |
| Novelty | It is identified whether an AE is expected (known) or unexpected (unknown) based on the precautions for Benet/Actonel. |
| Presence or absence of an AE | It is identified whether there is an AE (including “unknown”). |
| Presence or absence of an ADR | It is identified whether there is an ADR (including “unknown”). |
| Presence or absence of a SAE | It is identified whether there is a SAE (including “unknown”). |

6. Analysis Plan

Analysis sets, analysis items, and analysis methods are shown below. Details of variables for analysis and display will be specified in separately prepared statistical analysis specifications.

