 - Previous treatment group [Benet/Actonel (risedronate), bisphosphonate other than Benet/Actonel, calcium, vitamin D, osteoporosis drug not listed above (parathyroid hormone, anti-RANKL monoclonal antibody, other), steroid]
 - Presence or absence of concomitant medication [no, yes]
 - Disposition of concomitant medication [osteoporosis drug, anti-inflammatory analgesic, cardiovascular drug, central nervous system drug, antidiabetic, digestive system drug, other]
 - Combination therapy group [calcium, vitamin D, osteoporosis drug not listed above (parathyroid hormone, anti-RANKL monoclonal antibody, other), steroid]
 - Presence or absence of physical therapy [no, yes, unknown]
 - Presence or absence of other concomitant therapy (e.g., diet therapy, exercise therapy, block therapy) [no, yes, unknown]
 - Presence or absence of low back pain before the start of treatment [no, yes, unknown]
- 4) Analysis methods
- The number and proportion of patients will be calculated for the analysis item. Summary statistics will be calculated for analysis items with *1. Analysis items with *2 will be processed as specified in Section 5.1, “Handling of Dichotomous Variables.”

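### SAP Section 5.1 ignores a ticked 'Yes' that has no details, and the SAP does not say whether the same rule decides who is in the safety set

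*SAP*

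**What the plan says.** The references are to the current SAP, version 5.1, unless another version is named.

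- **Scope (SAP Section 5.1).** "For dichotomous variables, the presence or absence will be determined as described below when there is a column for details to be specified for" a 'Yes' answer. The sentence is general and names no variables.
- **Rule (SAP Section 5.1).** 'Yes' applies "when details are specified"; 'No' applies "when no details are specified and" the 'No' box is ticked; 'Unknown' applies "when neither 1 nor 2) is applicable".
- **Express use (SAP Section 6.1.2).** "Analysis items with *2 will be processed as specified in Section 5.1". The items so marked are concurrent illness, medical history other than fracture, and previous fracture. Each is tabulated as no, yes or unknown.
- **Safety set (SAP Section 4.3).** Exclusion criterion 2) is "Unknown whether an AE occurred". The efficacy set (4.4) is drawn from the safety set, and the vertebral-fracture set (4.5) from the efficacy set.
- **AE presence (SAP Section 5.5).** The flag reads "It is identified whether there is an AE (including" an unknown level). It has no algorithm and no pointer to Section 5.1.
- **AE data collected (Protocol Section 9.3).** "Presence or absence of AE (refer to Table 1), AE term, date of onset" and further items.

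**The concern.** The rule treats the two boxes differently. A bare 'No' is taken at face value, while a bare 'Yes', which is an explicit positive answer from the physician, is set aside. Data come on paper forms (Protocol Section 7.2), so blank detail fields are plausible, and the documents state no query rule for them.

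For the marked baseline items, a descriptive prevalence is at stake. For adverse events more could be at stake. If the same rule sets AE presence, a patient whose form says that an AE occurred would be classed as one for whom this is not known, and would leave the analysis sets on that ground. That would also run against SAP Section 3.2, where doubt is resolved towards counting: an event is serious if either source says so, and is a drug reaction unless both sources, or the only one available, call it unrelated.

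**Working it through.** The documents give no figure for this point, so there is none to reproduce. The check is a truth table, an illustration on assumed rates, and a comparison of the passages on scope.

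**1. The rule as written** (inputs: the three conditions in SAP Section 5.1)

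| Box ticked | Details written | Result |
|---|---|---|
| Yes | yes | Yes |
| Yes | no | Unknown |
| No | yes | Yes |
| No | no | No |
| none | yes | Yes |
| none | no | Unknown |

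Row 2 is the loss. Rows 3 and 5 work the other way: written details turn a 'No' or a blank into 'Yes'.

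**2. Size for a baseline item.** *N* = 500 is the planned total in Protocol Section 3.2. The share *p* ticking 'Yes' and the share *m* of those without details are assumptions.

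- Patients moved from 'Yes' to 'Unknown' = *N* × *p* × *m*
- Displayed 'Yes' share of all patients = *p* × (1 − *m*)
- Share of 'No' ticks carrying details that would cancel the loss = *p* × *m* / (1 − *p*)

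| *p* | *m* | Moved | 'Yes' shown | Cancelling share of 'No' ticks |
|---|---|---|---|---|
| 10% | 1% | 0.5 | 9.9% | 0.11% |
| 10% | 5% | 2.5 | 9.5% | 0.56% |
| 10% | 10% | 5 | 9.0% | 1.11% |
| 30% | 1% | 1.5 | 29.7% | 0.43% |
| 30% | 5% | 7.5 | 28.5% | 2.14% |
| 30% | 10% | 15 | 27.0% | 4.29% |
| 60% | 1% | 3 | 59.4% | 1.50% |
| 60% | 5% | 15 | 57.0% | 7.50% |
| 60% | 10% | 30 | 54.0% | 15.00% |

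For example, with *p* = 30% and *m* = 5%: 500 × 0.30 × 0.05 = 7.5 patients; 0.30 × 0.95 = 28.5%; 7.5 / 350 = 2.14%.

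**3. Does Section 5.1 reach AE presence?**

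Pointing towards yes:
- The scope sentence is general, and the AE item (presence, then term) has the shape it describes.
- SAP version 1.0 already carried the same rule. It had no baseline table and no efficacy analysis, and its only presence-or-absence variables were AE, ADR and SAE.
- The pointer from the baseline table to Section 5.1 is absent in version 4.0 and present in version 4.1, so it was added later and did not originally delimit the rule.

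Pointing towards no:
- The AE flag in Section 5.5 cites no rule, whereas its neighbours for relationship and seriousness cite Section 3.2.
- Section 4.3 2) does not cite Section 5.1 either.
- Processing is deferred to a separate data-set specification that is not among the documents.

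The text therefore permits the wider reading but does not state it.

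**4. If it does reach AE presence.** AE 'Yes' with no term → 'Unknown' → out of the safety set under 4.3 2) → out of the sets in 4.4 and 4.5. On the same assumed shares, 0.5 to 30 of 500 patients would go. The effect is on set membership and denominators. The safety tables in Section 6.2 classify events by SOC and PT, and an event without a term has no row there under any coding rule.

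**The case against.** The strongest case on the other side has five parts.

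- **Requiring details before counting a positive is a defensible, conservative convention.** That is fair for a descriptive table, but it does not explain why a recorded 'Yes' is treated like an empty field.
- **The rule also adds positives.** A reader might infer that prevalence is biased low. The documents do not support that: details override a 'No' or blank tick, and neither kind of entry has a stated frequency. This objection stands.
- **Nothing is hidden.** Section 5.3 shows the unknown category whenever it is populated, and Section 6.4.2 lists patients not evaluated with the reason and their AE status. This also stands, although visibility does not put a patient back in the 'Yes' count or in the safety set.
- **Little depends on the baseline items.** The efficacy analyses in Section 6.3 use none of them as a covariate or subgroup. A reader might think that the previous-fracture item affects eligibility, but entry to the vertebral-fracture set rests on baseline radiography (Section 4.5). This stands and limits the importance of the point.
- **The safety-set exclusion is an inference.** A reader might take it as the SAP's stated rule, or conclude that events vanish from the safety tables. Neither follows: no passage links the AE flag to Section 5.1, criterion 2) is an odd description of a form ticked 'Yes', and an event without a term could not be tabulated by SOC/PT anyway. What remains is that the SAP gives no other derivation, so a programmer could reasonably turn to Section 5.1.

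**Conclusion.** The point holds in a limited form, and it is minor. It is certain from the text that a ticked 'Yes' without details becomes 'Unknown', that a bare 'No' stands, and that each such 'Yes' is lost from the 'Yes' count of the three marked baseline items. The net direction and the size are not certain. The range of 0.5 to 30 patients in 500, or 0.1 to 6.0 percentage points, rests wholly on assumed rates.

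The consequence for the safety set is conditional on Section 5.1 governing AE presence. That reading is well supported but not expressed. If it applies, the harm is to denominators and to membership of the safety, efficacy and vertebral-fracture sets. Because those sets depend on it, the SAP should settle the question itself and not leave it to another document.

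**What to change.** In SAP Section 5.1:

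1. 'Yes' when details are specified, or when 'Yes' is checked and 'No' is not.
2. 'No' when no details are specified and only 'No' is checked.
3. 'Unknown' when no details are specified and neither box, or both boxes, are checked.

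The word 'only' in rule 2 matters. Simply adding the 'Yes' tick to rule 1 would let a form with both boxes ticked and no details satisfy 'Yes' and 'No' at once. The current rule codes that form as 'No'; the new one makes it 'Unknown'.

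In Section 6.1.2, add a details-unknown row to the disposition breakdowns, so that a bare 'Yes' has a place. In Section 5.5, state that AE presence follows the amended rule, so that a ticked AE 'Yes' never triggers criterion 2) of Section 4.3.

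The cost is a few phrases in the SAP and a small change in the derivation program. The only downside is the extra row. If the separate data-set specification already handles AE presence this way, only the sentence in Section 5.5 is needed for that part.
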